#### **4.2 Measurements**

For each patient, approximately ten milliliters of urine will be collected at zero, six, and twelve hours after transplantation, as well as, postoperative day one and two. Time zero will be defined as the time surgery is completed per documentation in the anesthesia flow sheet. Each sample will be placed in a centrifuge at 3300 RPM for three minutes. The urinary supernatant will be frozen at -80 Celsius and assayed in batches for NGAL and IL-18. Both urine NGAL and IL-18 will be quantified using ELISA testing. Serum and urine creatinine concentrations will be measured by the Jaffe assay using the P-module of a Cobas analyzer (Roche diagnostics, Indianapolis, IN) and the Beckman creatinine analyzer system (Beckman Instruments Inc., Fullerton CA).

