## **Remote Ischemic Preconditioning Study / Renal Transplant**

**PI: [name]**

**Co-Investigators:**

### **Specific aim:**

[figure not shown]
Remote ischemic preconditioning (RIPC), a phenotype of ischemic preconditioning, has been found to provide protection from I/R in humans. Several proof of concept clinical trials have shown that transient ischemia reperfusion of lower extremities confers protection to kidneys in patients undergoing endovascular or open surgical repair of an abdominal aortic aneurysm and in patients undergoing cardiac surgery. Furthermore, a randomized pilot clinical trial demonstrated that application of RIPC in high risk patients with kidney dysfunction undergoing coronary angioplasty reduced the incidence of procedure related contrast media induced AKI. To date the efficacy of RIPC in protecting renal allografts from I/R injury during renal transplantation has not been systematically investigated. **In this current proof of concept proposal we will test the central hypothesis that application of RIPC in donors and recipients during live donor kidney transplantation will reduce the severity of graft injury and improve outcome. We propose the following specific aim: To examine the effect of RIPC on clinical and biochemical markers of graft function in patients undergoing live donor kidney transplantation.**

In this study, patients undergoing live donor kidney transplantation will be allocated to the control group or RIPC group. Before allograft implantation, RIPC will be accomplished both in the donor and the recipient by inducing intermittent extremity ischemia through four five cycles of oscillometric blood pressure cuff inflation. The monitored clinical end points will include total urine output following kidney reperfusion over three days, plasma creatinine declination over five days, initiation of dialysis, and development of graft injury. Magnitude of graft injury will be measured using biochemical markers, such as, plasma and urinary concentration of neutrophil gelatinase associated lipocalin (NGAL), IL-18, and KIM-1. By rejecting our null hypothesis, RIPC may serve as a safe, cost-effective protective strategy to prevent allograft injury in the clinical setting of live donor kidney transplantation.

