#### **4.3 Outcomes**

The degree of allograft injury will be assessed by the levels of urinary biomarkers NGAL, IL-18, and KIM-

1. The primary endpoints will be the level of graft function in the early post transplantation period categorized as follows: delayed graft function (DGF) (defined as the need for dialysis within the first week of transplantation), slow graft function (SGF) (defined as <40% decrease in serum creatinine by POD 3), and immediate graft function (IGF) (defined as >40% reduction in serum creatinine by POD3). Incidence of allograft primary malfunction will be based on urine output during the first three days after

transplantation, the one month serum creatinine concentration, one month estimated GFR calculated according to diet modification. Additional secondary endpoints include 90 day mortality, length of ICU stay, and length of hospital stay.

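### Urinary biomarkers are compared as unindexed spot concentrations, with no planned check for dilution, although urine output is itself an outcome that RIPC may change

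*Combined protocol and SAP*

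**What the plan says.** **Biomarker scale.** The Specific aim measures graft injury by "plasma and urinary concentration of neutrophil gelatinase associated lipocalin (NGAL), IL-18, and KIM-1". Section 4.3 repeats this for urine: "The degree of allograft injury will be assessed by the levels of urinary biomarkers NGAL, IL-18", with KIM-1 named next. Neither place mentions a ratio to urine creatinine or an excretion rate.

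**Sampling.** Under Section 4.2, "approximately ten milliliters of urine will be collected at zero, six, and twelve hours after transplantation", and again on postoperative days one and two. These are spot samples, not timed collections. The same section adds that "Serum and urine creatinine concentrations will be measured by the Jaffe assay" and gives no purpose for the urine value. It describes no plasma sampling for the biomarkers.

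**Urine output.** The Specific aim lists "total urine output following kidney reperfusion over three days" among the clinical end points, and Section 4.3 uses urine output over the first three days to judge primary malfunction of the graft. The central hypothesis is that RIPC "will reduce the severity of graft injury and improve outcome".

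**Analysis.** Section 4.4 sizes the trial on a difference in mean NGAL per mL. It compares biomarkers, blood pressure, creatinine and urine output between arms by repeated-measures ANOVA. It names no covariate, no indexing and no sensitivity analysis for urine flow.

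**The concern.** The concentration of a substance in urine is its excretion rate divided by urine flow. Two arms with the same tubular injury and the same NGAL excretion will show different NGAL concentrations if one arm makes more urine. Randomisation does not remove this, because flow is determined after the intervention and may be changed by it.

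At stake is how a lower NGAL in the RIPC arm is read. The plan would take it as less injury, but part of it could be more urine. The plan's own reasoning makes this awkward: Sections 2.2.4 and 2.3 criticise serum creatinine partly because fluid volume influences it, and biomarkers are preferred on that account. Unindexed spot concentrations let a fluid effect back in.

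**Working it through.** **Step 1. The plan's sample size.** Inputs from Section 4.4: difference 35, SD 37, alpha 0.05, power 80%; 1:1 allocation from Section 4.1. Sidedness is not stated; two-sided is assumed.

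- Normal approximation: n = 2 × (1.96 + 0.84)² × 37² / 35² ≈ 17.5, rounded up to 18 per group.
- t-test: 18.55, rounded up to 19 per group, with 81% power at 19.
- A one-sided calculation gives 14 and does not match.

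The stated 19 per group is reproduced, so the trial is sized on the raw concentration scale.

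**Step 2. Shift from dilution alone.** Let C be the control-arm mean and f the ratio of urine flow, RIPC to control, with equal NGAL excretion in both arms. The RIPC mean is then C/f, so

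shift = C × (1 − 1/f).

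The plan gives no control-arm mean. Three assumed values span its own figures:

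- 49, the cited mean with immediate graft function;
- 84 = 49 + 35, which puts the RIPC arm at that mean;
- 248, the cited mean with slow graft function.

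The flow ratios 1.2 and 1.5 are also assumptions. For example, 84 × (1 − 1/1.2) = 14.0. The last column is the probability of a significant two-sided t-test with 19 per group and SD 37 when excretion does not differ.

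| Control mean C | Flow ratio f | Shift | Share of 35 | Chance of p < 0.05 |
|---|---|---|---|---|
| 49 | 1.2 | 8.2 | 23% | 10% |
| 84 | 1.2 | 14.0 | 40% | 21% |
| 248 | 1.2 | 41.3 | 118% | 92% |
| 49 | 1.5 | 16.3 | 47% | 26% |
| 84 | 1.5 | 28.0 | 80% | 62% |
| 248 | 1.5 | 82.7 | 236% | over 99% |

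**Step 3. Flow ratio that would produce the whole planned difference.** Setting the shift to 35 gives f = C/(C − 35):

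- C = 49: 49/14 = 3.5
- C = 84: 84/49 = 1.71
- C = 248: 248/213 = 1.16

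**Step 4. What a creatinine ratio would do.** The biomarker/creatinine ratio equals biomarker excretion divided by creatinine excretion, so urine flow cancels. Creatinine excretion does not. If better filtration in the RIPC arm raised it by 20% with NGAL excretion unchanged, the ratio would fall by 1 − 1/1.2 = 17%, in the same direction as dilution. The ratio is therefore informative but not decisive.

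**Limits of these figures.** They use one time point and a constant SD. The printed SD of 37 belongs to the immediate-function group. No SD is given for the slow-function group, and a larger one would lower the probabilities in the C = 248 rows. No sample size on an indexed scale can be derived, because the plan gives no mean or SD there.

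**The case against.** The case against has five parts, and most of it limits the point rather than removing it.

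- **A rise in urine output is not predicted.** A reader might infer that the plan expects RIPC to increase urine output. It says only that RIPC should improve outcome and lists urine output as an end point. The direction is a fair inference, not a stated expectation.
- **Urine creatinine may not be unused.** Section 4.4 lists creatinine without saying serum or urine, so urine creatinine might be compared between arms. What stands is narrower: no stated analysis uses it to correct the biomarkers.
- **Dilution would not be invisible.** A reader might conclude that lower NGAL could never be told apart from more urine. Urine output is recorded and compared between arms, so a difference in volume could be seen. But seeing it does not show how much of the NGAL difference it explains, and the plan specifies no analysis that does.
- **The magnitude is hypothetical.** The same 20% rise in flow gives 23% to 118% of the planned effect, depending only on the assumed control mean. At a mean of 49, even doubled flow gives a shift of 24.5, short of 35. This is right, so the range must be shown rather than one value.
- **Indexing is not a clean remedy.** Creatinine excretion is not steady after transplantation and depends on filtration, which RIPC may improve. Requiring raw and indexed results to agree could therefore pass a false positive. This also stands: the ratio should be supportive only, with an excretion-based check beside it.

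**Conclusion.** The point holds as a cheap improvement to the plan. The biomarker outcome that sets the sample size is an unindexed spot concentration, and no planned analysis separates an effect on injury from an effect on urine flow. With equal NGAL excretion, 20% more urine in the RIPC arm would shift NGAL by 8, 14 or 41, and 50% more by 16, 28 or 83, against a planned difference of 35. These figures rest on assumed control means (49, 84, 248) and assumed flow ratios; the documents do not show that any such difference in flow will occur.

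A reader might infer that the trial's primary result is compromised. The documents do not support that: Section 4.3 names delayed, slow or immediate graft function as primary, defined by dialysis and serum creatinine, which dilution of the urine does not touch. Nor is raw concentration a wrong choice of main biomarker scale. What is missing is a pre-specified check beside it.

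**What to change.** Keep raw concentration as the main biomarker analysis and say so in Section 4.4. Add there, before any data are seen, two supportive between-arm comparisons at the planned sampling times:

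1. the log of the biomarker/urine-creatinine ratio;
2. where urine output is recorded over an interval that covers the sample, approximate biomarker excretion: concentration × volume / time.

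Report both beside the raw result and the urine output by arm. State that a lower raw concentration will be described as reduced injury only with caution if these analyses do not support it. Do not make the creatinine-indexed result a formal condition for the claim.

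The cost is one or two extra models, with no new sample, assay or patient. Section 4.4 treats urine output as measured at multiple time points, but the plan does not say that the intervals match the sampling times, so (2) may be possible only for some samples. The ratio in (1) is supportive only, because creatinine excretion is unsteady after transplantation and rises with better filtration, which can bias the ratio in the same direction as dilution.

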#### **4.3 Outcomes**

The degree of allograft injury will be assessed by the levels of urinary biomarkers NGAL, IL-18, and KIM-

1. The primary endpoints will be the level of graft function in the early post transplantation period categorized as follows: delayed graft function (DGF) (defined as the need for dialysis within the first week of transplantation), slow graft function (SGF) (defined as <40% decrease in serum creatinine by POD 3), and immediate graft function (IGF) (defined as >40% reduction in serum creatinine by POD3). Incidence of allograft primary malfunction will be based on urine output during the first three days after

transplantation, the one month serum creatinine concentration, one month estimated GFR calculated according to diet modification. Additional secondary endpoints include 90 day mortality, length of ICU stay, and length of hospital stay.

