#### **4.4 Statistical Analysis**

The sample size calculation is based on a projected difference of NGAL levels between the two study arms. Hall et al reported a mean NGAL level of 49 mg/mL (SD = 37 mg/mL) for a group of patients that had immediate graft function and a mean NGAL level of 248 mg/mL in a group of patients with slow graft function. (which Hall reference is this) Based on these data we consider a conservative estimate of a mean difference between study groups to be 35 mg/mL NGAL. Using these assumptions, an alpha level of 0.05 and 80% power, we calculate a sample size of n= 19 per study group. Variables such as biomarkers, blood pressure, creatinine, and urine output that are expressed at multiple time points will be compared between the groups using repeated measures of ANOVA. Categorical variables will be expressed as percentages and will be compared using chi-squared analysis. A  $p$  value  $<0.05$  will be considered to be a statistically significant difference.

Ref#1 Perico(2004) delayed graft function in kidney transplantation Lancet 364(9447): 1814-1827 Perico, N., et al. (2004). "Delayed graft function in kidney transplantation." Lancet **364**(9447): 1814-1827

Ref #2 (old ref #11)

Ref#3 Rabb,H(2012) The promise of immune cell therapy for acute kidney injury.journal of clinical investigation122(11):3852-54(old ref #38)

Ref#4 Perico P (2004) Delayed graft function in kidney transplantation Lancet 364(9447):1814-1827

Ref#5 Siedlecki a etal(2011) Delayed graft function in kidney transplant Am j Transplant 11 (11) :2279-2296(old ref#42)

Ref#6 (OLD REF#6)

i Perico, N., et al. (2004). "Delayed graft function in kidney transplantation." *Lancet* **364**(9447): 1814-1827

ii Eltzschig ,H k and T.Eckle (2011). Ischemia and reperfusion –from mechanisms to translation *Nature Medicine* **17**(11) :1391-1401

iii Rabb,H(2012). The promise of immune cell therapy for acute kidney injury.*journal of clinical investigation***122**(11):3852-54

iv same as #1. Perico, N., et al. (2004). "Delayed graft function in kidney transplantation." *Lancet* **364**(9447): 1814-1827

v Siedlecki a etal. (2011). Delayed Graft Function in Kidney Transplant. *Am j Transplant* **11** (11) :2279-2296

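### Section 4.3 makes graft function (DGF/SGF/IGF) primary, but the 80% power and n=19 per group in 4.4 belong to NGAL alone and rest on the SD of immediate-function patients

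*Combined protocol and SAP*

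**What the plan says.** Section 4.3 uses the word primary once: "primary endpoints will be the level of graft function in the early post transplantation period categorized as follows", followed by DGF (dialysis in the first week), SGF and IGF (creatinine fall below or above 40% by day 3). The biomarkers have a separate sentence: "The degree of allograft injury will be assessed by the levels of urinary biomarkers NGAL, IL-18" and KIM-1.

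Section 4.4 opens with "The sample size calculation is based on a projected difference of NGAL levels between the two study arms". Its inputs are a mean of 49 with "SD = 37 mg/mL) for a group of patients that had immediate graft function", "a mean NGAL level of 248 mg/mL in a group of patients with slow graft function" with no SD, and a chosen difference of 35 (units as printed). It ends: "Using these assumptions, an alpha level of 0.05 and 80% power, we calculate a sample size of n= 19 per study group". Biomarkers and other variables "expressed at multiple time points will be compared between the groups using repeated measures of ANOVA"; section 4.2 schedules five urine samples. For graft function the plan names only a test: "Categorical variables will be expressed as percentages and will be compared using chi-squared analysis".

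Elsewhere, section 4 gives the trial's purpose as the effect of remote ischemic preconditioning (RIPC) on the magnitude of allograft injury. The Specific aim says that biochemical markers, NGAL among them, will measure that injury; it also lists clinical endpoints and calls the proposal proof of concept. Section 2.1 puts DGF at 4-10% of live-donor transplants.

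**The concern.** The trial's only power statement is not for the endpoint it calls primary. Sections 4 and 4.4 point to graft injury and 4.3 points to graft function, so a reader cannot tell which result decides the trial.

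Two consequences follow. A non-significant graft-function result could be read as evidence of no effect, although nothing in the plan shows that 19 per group could detect or usefully estimate one. And a significant NGAL result could be presented as the powered result, although NGAL was never declared primary.

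The NGAL power is itself conditional. Its SD comes from one function subgroup, whereas each trial arm will hold whatever mix of function occurs. Section 4.4 does not say to which sample time or repeated-measures contrast the 35 refers.

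**Working it through.** **1. The plan's own figure.** Inputs from 4.4: difference 35, SD 37, alpha 0.05 (taken as two-sided), 80% power. Allocation is 1:1 (4.1).

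- Normal approximation: n = 2 × (1.960 + 0.842)² × (37/35)² = 17.5, so 18 per group.
- t-test: n = 18.55, so 19 per group. At 19, the noncentrality is 35 / (37 × √(2/19)) = 2.92 on 36 degrees of freedom, and power is 81.0%. At 18 it is 78.7%.

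The stated 19 is reproduced for a single two-group comparison with SD 37.

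**2. NGAL when function is mixed.** Let a share f of each arm have slow function, with a gap g between the slow and immediate means. Assume SD 37 within each level, since the documents give no slow-group SD, and an RIPC shift of 35. Then SD = √(37² + f(1−f)g²). The documents give no value for f, so a range is shown. The gap in 4.4 is 248 − 49 = 199; a gap of 50 is an assumed alternative.

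| f (assumed) | g = 199: SD | power at 19 | n per group for 80% | g = 50: SD | power at 19 |
|---|---|---|---|---|---|
| 5% | 57.0 | 45% | 43 | 38.6 | 78% |
| 10% | 70.2 | 32% | 65 | 39.9 | 75% |
| 30% | 98.4 | 19% | 126 | 43.5 | 67% |
| 50% | 106.2 | 17% | 146 | 44.7 | 65% |

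Example, f = 5%, g = 199: 37² + 0.05 × 0.95 × 199² = 1369 + 1881 = 3250, whose root is 57.0.

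**3. NGAL as the mean of five samples.** With an assumed correlation of 0.5 within a function level, the SD of the mean is 37 × √((1 + 4 × 0.5)/5) = 28.7. If all recipients have immediate function, power is 96%. With 10% slow function and a gap of 199 lasting through all five samples, SD = √(28.7² + 0.09 × 199²) = 66.2 and power is 35%.

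**4. The declared primary: DGF component.** At 4-10%, 38 recipients yield 38 × 0.04 = 1.5 to 38 × 0.10 = 3.8 DGF cases if RIPC has no effect. Suppose RIPC eliminates DGF entirely. With 19 per group and no cases under RIPC, 3 v 0 gives chi-squared p = 0.071 and 4 v 0 gives p = 0.034 (no continuity correction), so at least 4 control cases are needed. The binomial probability of 4 or more among 19 is 0.6% at a 4% rate and 11.5% at 10%.

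**5. The declared primary: DGF+SGF against IGF.** The documents give no SGF rate, so both the control rates and the halving are assumptions. Exact enumeration of the uncorrected chi-squared test at 19 per group:

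| Control v RIPC | Power |
|---|---|
| 30% v 15% | 19% |
| 40% v 20% | 28% |
| 50% v 25% | 38% |

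The expected width of a Newcombe 95% interval for the difference in these three cases is 50-54 percentage points.

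**The case against.** The strongest defence is that the sample size fits the trial's purpose. Section 4 makes allograft injury the object of study, the Specific aim assigns its measurement to biomarkers, and section 2.3 rejects creatinine as a measure of graft injury. Section 4.4 says openly that its calculation is for NGAL, and a proof-of-concept trial need not be powered for a clinical category. Much of this stands. It makes the defect an internal inconsistency rather than a sample size without rationale, and it favours resolving it towards NGAL. It does not remove the inconsistency: 4.3 still gives primary status to graft function alone, and 4.4 does not use proof-of-concept status to justify 19 per group for that endpoint.

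The second defence is that the low power figures depend on assumptions. That also stands in part. The slow-function shares, the slow-group SD and the halving are not in the documents. Section 4.4 does not say whether the cited patients resemble these recipients or when they were sampled. With a smaller gap the loss of NGAL power is modest, and a repeated-measures contrast could exceed 80% if nearly everyone has immediate function. The mismatch between 4.3 and 4.4 needs none of these assumptions.

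Three stronger readings are tempting but not supported:

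- A reader might infer that n=19 is miscalculated. It reproduces.
- A reader might infer that the plan claims 80% power for graft function. It does not say so; it gives no power for graft function.
- A reader might infer that SD 37 can hold only if almost all recipients have immediate function. That requires the 199-unit gap to apply in this population at the analysed sample, which the documents do not establish.

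**Conclusion.** The concern holds as an inconsistency that should be repaired before data are seen. The endpoint called primary has no stated power or precision, and the endpoint with stated power is not called primary.

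For the primary, the figure closest to the documents is 0.6-11.5% power to detect complete elimination of DGF. It uses the protocol's own 4-10% rate but covers only one component of the endpoint. On assumed combined rates of 30-50%, a halving would be missed more often than detected.

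For NGAL, 81.0% is correct if the all-recipient SD is 37 and a single comparison is made. The text establishes that 37 describes one subgroup; how far the SD rises depends on the slow-function share and the gap. The illustrated single-comparison power runs from 78% (gap 50, 5% slow) to 17% (gap 199, 50% slow). The five-sample mean gives 96% if all have immediate function and 35% at 10% slow with a lasting 199 gap.

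**What to change.** Amend 4.3 and 4.4 so that one primary endpoint is named and the power statement belongs to it.

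**Route (a), the better fit to the Specific aim and sections 4 and 4.4.** Make urine NGAL the single primary endpoint. State the sample time or repeated-measures contrast to which the 35 refers. Make DGF/SGF/IGF secondary, reported with confidence intervals. Restate in 4.4 that 80% is conditional on an all-recipient SD of 37, and show power under larger SDs.

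**Route (b).** Keep graft function primary. Write an analysis rule that puts each recipient in exactly one level: as worded, a creatinine fall of exactly 40% is in none, and a dialysed recipient may also meet a creatinine definition. Give the power or expected confidence-interval width at 19 per group under stated DGF and SGF rates, and present the result as proof of concept.

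Either route is a wording change and requires no added patients or assays. The cost is a less favourable stated power: under (a) the 80% becomes conditional, and under (b) the primary result is openly an estimate with a wide interval. Neither route by itself secures 80% power. If 80% is required, the sample size must be recalculated for the chosen endpoint.

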#### **4.1 Randomization and intervention**

Patients undergoing live-donor renal transplant will be randomized to the RIPC or the control group in a 1:1 ratio using manually shuffled blocks of ten generated by the study coordinator. The allocation sequence will be concealed until the study group is assigned. The study coordinator will open the opaque sealed envelope containing the patients' group before the patient arrives at the operating room. For patients randomized to RIPC, a tourniquet (Stryker, Kalamazoo MI) will be placed on the lower or upper extremity avoiding the intraoperative blood pressure cuff and any functioning dialysis-access fistula. The

tourniquet will be inflated 3 times to a pressure of 200mmHg for five minutes with five minutes of reperfusion between inflations. The RIPC regimen will be administered while patient monitors, intravascular catheters and indwelling bladder catheters are being placed in order not to affect the time from induction of anesthesia to initial skin incision compared with the control group. Tourniquet cuff pressures of 20 mmHg applied to control group patients will provide some level of compression without ischemia. All patients will receive standard perioperative and postoperative care as directed by the anesthesiology and surgical staff with all receiving isoflurane as part of the anesthetic technique.

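### Cutting the creatinine fall at 40% and testing the three graft-function classes by unordered chi-squared costs much power at 19 per arm if RIPC improves recovery generally; it does not if RIPC only moves recipients between well-separated classes

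*Combined protocol and SAP*

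**What the plan says.** Section 4.3 (Outcomes) states: "The primary endpoints will be the level of graft function in the early post transplantation period categorized as follows". The classes are DGF (dialysis in the first week), SGF and IGF. The section gives "slow graft function (SGF) (defined as <40% decrease in serum creatinine by POD 3", and IGF is a fall of more than 40% by the same day. It names no baseline for the percent fall, and a fall of exactly 40% belongs to neither class.

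Section 4.4 (Statistical Analysis) states: "Categorical variables will be expressed as percentages and will be compared using chi-squared analysis". No ordered or ranked test appears. Variables measured at several time points, creatinine among them, are compared by repeated-measures ANOVA, and the Specific aim lists the creatinine decline over five days among the monitored endpoints. Neither is named primary.

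The sample size was set on NGAL: "a mean difference between study groups to be 35 mg/mL NGAL", an SD taken from "a mean NGAL level of 49 mg/mL (SD = 37 mg/mL", "an alpha level of 0.05 and 80% power", and hence "we calculate a sample size of n= 19 per study group". Allocation is "randomized to the RIPC or the control group in a 1:1 ratio". The documents give no SGF rate, target difference or power for the primary endpoint. Section 2.1 puts live-donor DGF at 4-10%.

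**The concern.** In the primary test a recipient whose creatinine falls 41% counts the same as one whose creatinine falls 85%, and 39% counts the same as 0%. Two kinds of information go unused: how far creatinine fell within a class, and the fact that DGF is worse than SGF and SGF worse than IGF. The central hypothesis is that RIPC reduces the severity of graft injury, which reads as a graded effect. With 19 per arm and live-donor DGF of 4-10%, only one or two control recipients would be expected to need dialysis (19 × 0.04 = 0.8; 19 × 0.10 = 1.9). The test would therefore rest mainly on who crosses 40%. At stake is a null primary result in a trial where function had improved across recipients.

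**Working it through.** **1. The plan's own figure.** The standardized NGAL effect is 35/37 = 0.946 SD. A two-sided two-sample t test at alpha 0.05 and 80% power needs 18.55, rounded up to 19 per arm (power 0.81 at 19). The figure reproduces, for NGAL only. Sidedness is not stated; two-sided is assumed.

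**2. Model for a general improvement.** Inputs from the documents: 19 per arm, the three classes, chi-squared, alpha 0.05, and DGF 4-10%. Assumptions: control DGF 7% (the middle of that range), control SGF 13%, 23% or 33%, and a shift of *d* SD in early function for every recipient. Early function is normal in controls and cut at z = Φ⁻¹(0.07) and z = Φ⁻¹(0.07 + SGF). The RIPC share below a cut is Φ(z − d).

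At d = 0.8:
- DGF: Φ(−1.476 − 0.8) = 1.1%, against 7%.
- DGF + SGF: Φ(−0.842 − 0.8) = 5.0% against 20%. By the same formula, 9.3% against 30% and 14.6% against 40%.

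**3. Power by simulation, 19 per arm, 4,000 trials per scenario.** The Monte Carlo standard error is at most √(0.25/4,000) = 0.8 points. The ranked test is Wilcoxon rank-sum on the percent fall, with DGF tied at the worst rank. Columns are control SGF 13% / 23% / 33%.

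| Shift | Chi-squared, 3 classes | Ordered 3-class | Ranked fall |
|---|---|---|---|
| 0.5 SD | 6 / 12 / 14% | 15 / 20 / 21% | about 30% |
| 0.8 SD | 11 / 23 / 31% | 27 / 36 / 43% | about 64% |
| 0.946 SD (NGAL effect, borrowed) | 13 / 30 / 40% | 32 / 46 / 53% | about 78% |

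With no effect, the ranked test rejects in 4.4-4.8% of trials, so its gain is not inflated type I error.

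**4. Splitting the gap at 0.8 SD.**
- Total gap, chi-squared to ranks: 64 − 11 = 53, 64 − 23 = 41 and 64 − 31 = 33 points.
- Recovered by using class order: 27 − 11 = 16, 36 − 23 = 13 and 43 − 31 = 12 points, or 30%, 32% and 36% of the gap.
- The remainder (37, 28 and 21 points) comes from the cut.

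**5. Check by formula.** Collapse to IGF against the rest, with d = 0.946. For 80% power, n per arm = [1.96√(2p̄(1−p̄)) + 0.84√(p₁(1−p₁) + p₂(1−p₂))]² / (p₁−p₂)². With 20% against 3.7% this is 61; with 30% against 7.1%, 44; with 40% against 11.5%, 36. The ranked fall needs about 20.

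**6. The opposite model.** Let RIPC only move recipients between classes, with SGF and IGF falls not overlapping and no change within a class.

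| DGF/SGF, control v RIPC | Chi-squared | Ordered 3-class | Ranked fall |
|---|---|---|---|
| 7/33% v 3/12% | 31% | 40% | 25% |
| 7/40% v 3/10% | 54% | 61% | 41% |
| 7/23% v 2/10% | 16% | 27% | 14% |

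Here ranking the fall is the weakest of the three tests and the ordered three-class test is the best.

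**The case against.** The strongest objection is that the gain depends on an effect model that the documents do not supply. The shift and the SGF rates are assumed, and no passage says how many live-donor recipients exceed 40%. The plan's own NGAL figures hint at separated states: 248 with slow function against 49 with immediate function is (248 − 49)/37 = 5.4 SDs of the immediate-function group. If RIPC rescues some recipients from slow function and leaves the rest alone, ranking loses. This stands and limits the conclusion. It does not settle the matter, because those figures are NGAL rather than creatinine and no SD is given for slow function.

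Second, a reader might infer that the plan throws away the magnitude of the creatinine fall. It does not: the repeated-measures ANOVA uses it. What stands is that this analysis is not primary, and Section 4.4 gives no rule for creatinine in dialysed recipients.

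Third, a reader might blame the whole loss on the 40% cut. Step 4 shows that about a third comes from a test that ignores class order.

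Fourth, Section 2.3 warns that creatinine also reflects body weight, muscle mass, protein intake and fluid volume, so differences between recipients are not purely graft function. That is fair, and the simulation does not model this noise separately. The classes rest on the same creatinine values, but noise alters a class mainly near the cut, while it can reorder any ranked recipient.

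**Conclusion.** The point holds in conditional form. If RIPC improves early function across recipients, the planned primary test gives up a large share of the available power: at 0.8 SD, about 11-31% against 64% for the ranked fall, with an ordered three-class test between them at 27-43%. The direction held at 0.5, 0.8 and 0.946 SD and at every SGF rate tried. The sizes rest on assumed SGF rates and an assumed shift; only the DGF range comes from the documents.

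Two stronger readings are not supported. One is that the class endpoint always has less power than ranks: in the examples with separated classes the ranked test is lower by 31 − 25 = 6, 54 − 41 = 13 and 16 − 14 = 2 points. The other is that ranking makes 19 per arm adequate for the primary endpoint: ranked power is about 30% at 0.5 SD and only comes near 80% at about 0.95 SD. The graded wording of the central hypothesis is the reason to prefer the ranked test as primary.

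**What to change.** Keep the DGF/SGF/IGF table as the description of the primary endpoint. Prespecify one primary test, a Wilcoxon rank-sum on one rank per recipient. Recipients dialysed in the first week share the worst rank; all others are ordered by percent creatinine fall from the pre-transplant value to POD 3. Report the win probability (the chance that a random RIPC recipient ranks better than a random control, ties counted half) with a 95% confidence interval. Report an ordered three-class test as a supporting analysis, in place of the unordered chi-squared, to cover an effect that lies in class changes. State the baseline for the percent fall; the ranking then also places a fall of exactly 40%.

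The cost is wording in Sections 4.3 and 4.4. No new data are needed, because the percent fall must be computed to assign the classes. There are two downsides. The headline becomes a rank comparison rather than class percentages, which is a different summary of the effect and should be shown beside the table. Power is also lower than with the class tests if the effect lies only in crossing 40%.
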